6.4 Radiation Therapy Toxicity Assessment During Therapy

Expected toxicities from SBRT are listed in Section 7.1.1.2. Patients will be assessed at least once during radiation therapy for toxicity. Radiation therapy will continue as planned as long as there is no grade 3 or 4 toxicity, bilirubin is <51 mmol/L, Child score is A5-6 and the treating physician recommends continuation. Otherwise, a delay in radiation therapy should occur with possible

continuation of radiation if it resolves. If there is evidence of rapid changes in liver function suggestive of developing toxicity, or if the investigator has concerns regarding the clinical status of the subject, a delay in radiation therapy should be considered even if the criteria below are not met.

If the patient discontinues radiation therapy prematurely, the patient may be considered for further pembrolizumab, if criteria for treatment (see Section 6.1) are met within the allowed time window, and at the discretion of the treating Investigator.

Table 9: Radiation Therapy Toxicity and Suggested Modification

Toxicity	Modification
Hematologic Toxicities	
Grade 1-2	Continue radiation
Grade 3	Hold radiation until \leq grade 2, then resume
Grade 4	Hold radiation 1 week and until \leq grade 2, then resume
Gastrointestinal Toxicities	
Grade 1-2	Continue radiation
Grade 3-4 diarrhea	Hold radiation until \leq grade 2, then resume
Grade 1-2 nausea or vomiting	Initiate anti-emetics prior to radiation and as needed and continue radiation
Grade 3 nausea or vomiting	Hold radiation until \leq grade 2, then resume with anti-emetics prior to radiation and as needed
Hepatic Dysfunction	
Bilirubin 22-51 umol/L	Continue radiation
Bilirubin > 51 umol/L	Hold radiation until bilirubin improves to ≤ 51 mmol/L; treat as per hepatic ECI (Section 6.2) Consider resuming radiation only if rapid improvement.
Grade 1-2 AST/ALT	Continue radiation
Among subjects with baseline ALT $< 2 \times$ ULN: ALT $\geq 5 \times$ ULN	Hold radiation until bilirubin improves to \leq grade 2; treat as per hepatic ECI (Section 6.2). Consider resuming radiation only if rapid improvement
Among subjects with baseline ALT $\geq 2 \times$ ULN: ALT $> 3 \times$ the baseline level	
Child-Pugh Score > 7	Hold radiation until improves to Child-Pugh Score ≤ 7
Other non-hematologic toxicities	
Grade 1-2	Continue radiation
Grade 3	Hold radiation until improves to \leq grade 2, then resume
Grade 4	Discontinue radiation

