5.1.2.1 Prescription Dose

Absorbed dose: 27.5 Gy - 50 Gy in 5 fractions. The prescription dose may be 50 Gy, 45 Gy, 40 Gy, 35 Gy, 30 Gy or 27.5 Gy in 5 fractions, based on normal tissue constraints. The dose to multiple PTVs may be different. The goal is to use the highest allowable prescription dose to the primary target, while respecting normal tissue constraints. The minimal planned prescription dose to PTVs is 27.5 Gy. Given the novelty of this combination, and the potential for overlapping hepatic toxicity, the first 10 patients will have to meet all the following additional liver dosimetric constraints:

- 1) Mean liver (minus gross HCC tumor volume) dose < 15 Gy in 5 fractions.
- 2) $D_{800cc} \leq 18$ Gy in 5 fractions
- 3) Biologically corrected normal tissue complication probability (NTCP) $< 0.5\%$

If 2 or fewer patients of the first 10 patients experience grade 3 hepatic toxicity at this dose, we will increase to standard dosing. If 3 or more patients experience grade 3 toxicity, or if any patients experience grade 4/5 toxicity in first 3 months following SBRT, these dose constraints will be maintained for all patients on study and modification of all SBRT dose constraints will be considered.

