6.2 Guidance for Diagnosis and Management of Hepatic Events of Clinical Interest (ECIs)

In addition to overdose, hepatic ECIs will include any of the following events. All of these events will require holding pembrolizumab treatment and notification of the Sponsor within 24 hours. Refer to Section 7 for reporting guidelines.

All cases of retreatment and permanent discontinuation must be reported to the Sponsor and recorded in the database.

a) ALT:

- i) Among subjects with baseline ALT $<2 \times \text{ULN}$: ALT $\geq 5 \times \text{ULN}$
- ii) Among subjects with baseline ALT $\geq 2 \times \text{ULN}$: ALT $> 3 \times$ the baseline level
- iii) ALT $> 500 \text{ U/L}$ regardless of baseline level

(Subjects with ALT $> 5 \times \text{ULN}$ at baseline are not eligible for enrollment)

b) AST:

- i) Among subjects with baseline AST $<2 \times \text{ULN}$: AST $\geq 5 \times \text{ULN}$
- ii) Among subjects with baseline AST $\geq 2 \times \text{ULN}$: AST $> 3 \times$ the baseline level
- iii) AST $> 500 \text{ U/L}$ regardless of baseline level

(Subjects with AST $> 5 \times \text{ULN}$ at baseline are not eligible for enrollment)

c) Total Bilirubin:

- i) Among subjects with baseline levels $< 22 \text{ umol/L}$: a value of $> 34 \text{ umol/L}$
- ii) Among subjects with baseline levels that are $\geq 22 \text{ umol/L}$: a value $\geq 2 \times$ the baseline level
- iii) Total bilirubin $> 51 \text{ umol/L}$ regardless of baseline level

(Subjects with total bilirubin $> 34 \text{ umol/L}$ at baseline are not eligible for enrollment)

d) Regardless of laboratory values, hepatic decompensation diagnosed clinically, including:

- i) New onset clinically detectable ascites
- ii) Gastrointestinal bleeding suggestive of portal hypertension (e.g., esophageal or gastric varices)
- iii) Encephalopathy

(Subjects with clinically apparent ascites or encephalopathy, or untreated varices at baseline are not eligible for enrollment)

Immediate assessment

All subjects

- All subjects should be evaluated according to directions below within 72 hours of alert for non-overdose ECI
- Procedures:
 - Obtain an opinion from a hepatologist
 - Obtain a work-up for hepatitis if there is no underlying hepatitis, including hepatitis A, B, C, D, Epstein-Barr virus serology, and cytomegalovirus serology

- Assess for ingestion of drugs/supplements with hepatotoxic potential
- Assess for alcohol ingestion

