2) HCV Flare:

- At the time of first detection of HCV RNA, send a specimen for HCV genotyping
- Measure AST, ALT, ALP, bilirubin, INR weekly
- Measure HCV RNA levels every 2 weeks
- Therapy with HCV anti-viral treatments should be strongly considered.

3) For both recurrent infection and HCV flare: if ALT returns to normal or Grade 1 (if normal at baseline), or to baseline grade (if Grade 2 at baseline) within 12 weeks, and the subjects are clinically stable, subjects may restart pembrolizumab treatment. If these conditions are not met, then pembrolizumab treatment should be permanently discontinued.

c. Immune-related hepatitis

1) Description

Immune-related hepatitis due to pembrolizumab should be suspected if any of the following is seen:

- AST or ALT baseline values are less than $2\times$ ULN, and AST or ALT laboratory values increase to $\geq 5\times$ ULN
- Among subjects with baseline ALT or AST $\geq 2\times$ ULN, levels increase to $>3\times$ the baseline level
- AST/ALT >500 U/L regardless of baseline level
- Among subjects with baseline levels <22 umol/L: a value of >34 umol/L
- Among subjects with baseline levels that are ≥ 22 umol/L: a value $\geq 2\times$ the baseline level
- Total bilirubin >51 umol/L regardless of baseline level

Immune-related hepatitis is a diagnosis made after excluding other possible etiologies for the change. Viral flare (if applicable), biliary or vascular obstruction, infection, medications, and alcohol use must be ruled out (see below).

2) Management

- Interrupt pembrolizumab treatment.
- Start IV corticosteroid (methylprednisolone 1-2 mg/kg/day) followed by oral corticosteroid (1-2 mg/kg/day).
- Monitor with biweekly laboratory tests including AST, ALT, bilirubin, ALP, and INR.
- If symptoms and laboratory tests resolve to Grade ≤ 1 or baseline (if abnormal at baseline), taper steroids over 28 days. Pembrolizumab treatment may be restarted after steroid treatment has been tapered to prednisone ≤ 10 mg/day (or equivalent dose of another agent).
- If laboratory abnormalities do not resolve within 3 weeks, or steroids cannot be lowered to ≤ 10 mg/day (or prednisone equivalent) within 12 weeks, or subjects show evidence of decompensation to CP C status or have esophageal or variceal bleeding at any point, treatment must be permanently discontinued.
- Consultation with a hepatologist is advised

d. Other Hepatic Events of Clinical Interest

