APPENDIX 2 CHILD-PUGH SCORE

The Child-Pugh score is used to assess the prognosis of chronic liver disease, mainly cirrhosis. Although originally designed to predict mortality after surgery, it is now used to determine prognosis and eligibility for treatment as well as the need for future liver transplantation.

The score employs five clinical measures of liver disease. Each measure is scored between 1 and 3, with 3 indicating most severe derangement. The scores are then added to form a total.

Measure	1 point	2 points	3 points
Bilirubin (umol/L)	<34	34-51	>51
Albumin (g/L)	>35	28-35	<28
INR	<1.7	1.7-2.3	>2.3
Ascites	None	Easily controlled	Poorly controlled
Hepatic encephalopathy ¹	None	Grade I-II (mild or moderate)	Grade III-IV (severe or coma)

Points	Class	One year survival	Two year survival
5-6	A	100%	85%
7-9	B	81%	57%
10-15	C	45%	35%

¹ Hepatic encephalopathy graded according to West Haven Criteria for Semi-quantitative Grading of Mental Status: *Adapted from: Conn H, Lieberthal M. The hepatic coma syndromes and lactulose. Baltimore: Williams & Wilkins; 1979.*

- Grade I: Trivial lack of awareness; euphoria or anxiety; shortened attention span; impaired performance of addition or subtraction
- Grade II: Lethargy or Lethargy or apathy; minimal disorientation for time or place; subtle personality change; inappropriate behavior
- Grade III: Somnolence to semi-stupor, but responsive to verbal stimuli
Confusion; Gross disorientation
- Grade IV: Coma (unresponsive to verbal or noxious stimuli)

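### Section 6.4 prints two bilirubin limits for SBRT (to continue, and to release a hold) in mmol/L, 1000 times the 51 umol/L hold trigger: a minor safety correction

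*Combined protocol and SAP*

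**What the plan says.** The narrative of Section 6.4 sets conditions for SBRT to proceed as planned: no grade 3 or 4 toxicity, and "bilirubin is <51 mmol/L, Child score is A5-6 and the treating physician recommends continuation". If these are not met, radiation is to be delayed and may go on once the problem resolves.

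Table 9, under Hepatic Dysfunction, deals with bilirubin in two rows:

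- The row "Bilirubin 22-51 umol/L" says to continue.
- The row for values above 51 umol/L says to hold until bilirubin is at or below "51 mmol/L; treat as per hepatic ECI (Section 6.2"), and adds: "Consider resuming radiation only if rapid improvement".

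A further Table 9 row holds radiation at a Child-Pugh score above 7 and releases it at 7 or below.

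Section 6.2 uses the same number, 51, in umol/L. Its list of signs of immune-related hepatitis includes "Total bilirubin >51 umol/L regardless of baseline level", and the same threshold defines a hepatic event of clinical interest. For those events, "All of these events will require holding pembrolizumab treatment and notification of the Sponsor within 24 hours".

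**The concern.** The two limits in mmol/L decide when SBRT may carry on and when a held course may restart. Taken literally, a patient whose radiation has just been held for bilirubin of 60 umol/L already satisfies the release limit, and the limit in the text would not have stopped treatment either. The protocol itself tightens the liver dose constraints for the first 10 patients because of its worry about liver injury (Section 5.1.2.1): "Given the novelty of this combination, and the potential for overlapping hepatic toxicity". Limits on continuing and restarting liver radiation should therefore be right as printed, even where a clinician would probably guess the correct value.

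**Working it through.** There is no design figure to reproduce. The check is a unit conversion, a count of units, and a comparison of the rules at selected values.

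**Size of the discrepancy.** Inputs: 51 mmol/L (Section 6.4 text and Table 9 release limit), 51 umol/L (Table 9 hold trigger), 34 umol/L (entry ceiling, Section 3.1.12, Table 1).

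- 51 mmol/L × 1000 = 51,000 umol/L
- 51,000 / 51 = 1000 times the hold trigger
- 51,000 / 34 = 1500 times the entry ceiling

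**Intended unit.** Bilirubin mentions with a unit:

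- umol/L: Synopsis 1, Section 3.1.12 Table 1 1, Section 6.2 event definitions 5, Section 6.2 immune-related hepatitis 4, Table 9 2, Appendix 2 1. Total 1 + 1 + 5 + 4 + 2 + 1 = 14.
- mmol/L: Section 6.4 text 1, Table 9 release limit 1. Total 2.

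**Rules at selected values, bilirubin alone:**

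| Bilirubin (umol/L) | Text limit as printed | Text limit in umol/L | Table 9 action | Release limit as printed | Release limit in umol/L |
|---|---|---|---|---|---|
| 50 | met | met | continue | met | met |
| 51 | met | not met | continue | met | met |
| 60 | met | not met | hold | met | not met |
| 200 | met | not met | hold | met | not met |

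As printed, the text limit first fails at 51,000 umol/L. With the unit corrected, the Table 9 row is coherent: hold above 51, release at or below 51. Text and table then disagree in one line only, at exactly 51.

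**Child-Pugh condition.** Appendix 2 has five measures: "Each measure is scored between 1 and 3, with 3 indicating most severe derangement".

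- Bilirubin above 51 umol/L scores 3, so the minimum total is 3 + 1 + 1 + 1 + 1 = 7. The text's A5-6 condition cannot be met, and so backs up the missing bilirubin limit.
- Bilirubin of exactly 51 umol/L scores 2, so the minimum total is 2 + 1 + 1 + 1 + 1 = 6. A5-6 can be met and does not settle the disagreement at 51.
- Bilirubin of 34 to 51 umol/L plus one other 2-point item gives 2 + 2 + 1 + 1 + 1 = 7. The text calls for a delay, while Table 9, which holds only above 7, does not hold on the score.

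**The case against.** The strongest reply is that this is a slip with an obvious reading. The two neighbouring Table 9 entries are in umol/L, and Section 6.2 uses 51 umol/L. The hold trigger is right. Other controls also apply: the bar on grade 3 or 4 toxicity, the A5-6 condition, the physician's recommendation, the advice to consider a delay when liver function changes rapidly, the restriction on resuming, and hepatic event management. Table 9 is also headed as suggested modifications. All of this stands, and it makes the point minor. It does not make the printed limits correct.

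A reader might go further in four ways that the documents do not support:

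- That patients are left without protection, or that the section cannot be used. The correct trigger and the other conditions still operate.
- That text and table conflict at 51 as printed. Read literally, 51 umol/L is far below 51 mmol/L and both say continue. The mismatch appears only once the unit is corrected.
- That the text should become at or below 51. That would relax the stricter rule, and the documents give no clinical reason for it. Changing the table would be equally consistent.
- That after correction SBRT simply continues up to 51 umol/L. The other conditions in the text can still require a delay, as the score of 7 above shows.

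Conversion of a PDF to text can also turn a micro sign into an m. That is unlikely here, because the same row prints umol/L with a plain u and Greek letters survive elsewhere in the document, but it is not excluded.

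**Conclusion.** The point holds as a minor safety correction. Two limits in Section 6.4 are too high by a factor of 1000 as printed and so restrict nothing. The intended value, 51 umol/L, is clear from the same row and from the rest of the protocol. The documents give no expected number of patients above 51 umol/L during the five fractions, so the number of decisions at risk cannot be stated; given the remaining safeguards it should be small. The conclusion assumes that the source page does print mmol/L.

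Only the unit correction is settled. The disagreement at exactly 51 umol/L follows from that correction and concerns a single value. The difference between A5-6 in the text and the hold above 7 in Table 9 is already there as printed, and leaves a score of 7 treated in two ways. Neither bears on sample size, error rates or the primary analysis.

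**What to change.** 1. Check the source page. If it prints mmol/L, change it to umol/L in the Section 6.4 text and in the Table 9 release limit, and notify the site.
2. In the same edit, align text and table at exactly 51 umol/L in whichever direction the investigators prefer clinically. By default keep the stricter text rule (below 51) and adjust the Table 9 rows to it.
3. Reconcile the text's A5-6 condition with Table 9's Child-Pugh hold above 7, so that a score of 7 has one stated action.

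The cost is two unit changes, one boundary and one Child-Pugh threshold in the next amendment, plus a short note to the site. Items 2 and 3 need a brief clinical decision; item 1 does not.

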3. SUBJECT SELECTION

3.1 Inclusion Criteria

In order to be eligible for participation in this trial, the subject must:

- 3.1.1 Be willing and able to provide written informed consent/assent for the trial.
- 3.1.2 Be ≥ 18 years of age on day of signing informed consent.
- 3.1.3 Have a histologically or cytologically confirmed diagnosis of hepatocellular carcinoma, and at least one measurable lesion as defined by RECIST 1.1/iRECIST. Otherwise eligible subjects, with a radiographic diagnosis of HCC, may be enrolled for screening, but histological confirmation is mandatory prior to initiation of study therapy.
- 3.1.4 Have current liver function meeting Child Pugh Class A (5-6 points), with no encephalopathy or ascites. Child Pugh status must be calculated based on clinical and laboratory results during the screening period.
- 3.1.5 Have intrahepatic HCC amenable to SBRT:
 - maximum 10 lesions to be treated, and
 - total tumor diameter to be treated <20 cm
 - No single liver tumor >15 cm in diameter
 - No evidence of common or main branch bile duct invasion
 - No evidence of direct tumor extension into stomach, duodenum, small bowel, large bowel or diaphragm
 - Smaller satellites of HCC or non-definite HCC need not be encompassed within SBRT volumes if needed to respect normal tissue limits.
- 3.1.6 Be willing to provide tissue from a newly obtained core or excisional biopsy of a tumor lesion. Newly-obtained is defined as a specimen obtained up to 6 weeks (42 days) prior to initiation of treatment on Day 1. The subject must have a site of disease amenable to biopsy, and be a candidate for tumor biopsy. In addition, the subject must be willing to give blood for correlative studies, and have no contraindications to this.
- 3.1.7 Have a performance status of 0 or 1 on the ECOG Performance Scale.

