AFP	X	X			X	X	X	X	X	X	
Biopsy for correlative studies	X										
Optional biopsy for correlative studies					X ^k						
Blood for ctDNA/methylation ^l		X		X				X		X	
Blood for cytokine analysis ^l		X		X	X	X		X		X	
Survival status											X

All assessments may be performed up to 2 working days prior to scheduled day.

A: Pembrolizumab 200 mg IV Q3W
 B: SBRT as per Section 5.1.2, commencing Cycle 1 Day 2, consisting of 5 fractions over 5-15 days
 a: Albumin, alkaline phosphatase, total bilirubin, bicarbonate, calcium, chloride, creatinine, glucose, LDH, phosphorus, potassium, total protein, AST, ALT, sodium.
 b: Serum pregnancy test (women of childbearing potential).
 c: See Section 5.4 for post-treatment follow-up requirements.
 d: Blood pressure, temperature, pulse, O₂ saturation, and respiratory rate.
 e: Day of assessment while on SBRT may vary due to weekends, but should be as close to day 3 as possible.
 f: See Appendix 4 for vascular thrombosis staging chart.
 g: All patients should have baseline Hepatitis B screening which should include: HbsAg, Anti-Hbs and Anti-Hbc (total+IgM). For patients with known hepatitis B, or if they have been deemed infected through baseline screening, additional test should include: HBV viral load (DNA), HbeAg and Anti-Hbe. If HBV viral load has been performed within previous 3 months a repeat test is not required. If Hepatitis B Testing has been performed for eligibility less than 28 days prior to start of therapy it is not required to be repeated again as a part of Baseline (Pre-study) evaluations.
 h: All patients should have baseline Hepatitis C screening which should include: Anti-HCV. For patients with known hepatitis C, or if they have been deemed infected through baseline screening, HCV viral load (RNA) should be performed. If HCV viral load has been performed within previous 3 months a repeat test is not required. If Hepatitis C Testing has been performed for eligibility less than 28 days prior to start of therapy it is not required to be repeated again as a part of Baseline (Pre-study) evaluations.
 i: Patients who come off study treatment for reasons other than radiological progression are to have tumor measurements and disease response evaluated every 3mo ± 14 days until documented progression per iRECIST or start of new therapy.

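### Section 6.4 gives two Child-Pugh rules for holding and restarting SBRT, and they disagree at a score of 7

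*Combined protocol and SAP*

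**What the plan says.** The opening text of Section 6.4 lists conditions that must all be met for SBRT to go on as planned: no grade 3 or 4 toxicity, a bilirubin limit of 51, and "Child score is A5-6 and the treating physician recommends continuation". If they are not met, the instruction is "Otherwise, a delay in radiation therapy should occur with possible" "continuation of radiation if it resolves". No restart score is given.

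Table 9, in the same section, has its own Child-Pugh row. The trigger is a score above 7, and the action is "Hold radiation until improves to Child-Pugh Score" 7 or less. A separate row, "Bilirubin 22-51 umol/L", tells the team to carry on with radiation.

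Three other places bear on this:

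- Section 3.1.4 requires patients to "Have current liver function meeting Child Pugh Class A (5-6 points), with no encephalopathy or ascites".
- Appendix 2 defines the score: five measures, where "Each measure is scored between 1 and 3, with 3 indicating most severe derangement". Totals of 5-6 are class A and 7-9 are class B.
- The Section 10 calendar schedules one Child-Pugh score during SBRT. Its note says "Day of assessment while on SBRT may vary due to weekends, but should be as close to day 3 as possible".

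**The concern.** A score of 7 is class B. It fails the text's condition for continuing, yet it does not reach the table's trigger for holding. It is also low enough for the table to end a hold that is already in place. At 7, two clinicians could do opposite things and both be following Section 6.4, and a monitor could not call either one a deviation.

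This is a liver-safety rule. Section 5.1.2.1 tightens the liver dose limits for the first 10 patients because the drug and the radiation may both injure the liver. Section 2.2.3 reports no clinical experience of anti-PD-1 treatment with SBRT in liver cancer. Section 2.2.2 names baseline A6 versus A5 as a factor significantly associated with SBRT toxicity. Patients enter at 5 or 6, so an A6 patient reaches 7 by losing one point and an A5 patient by losing two.

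**Working it through.** The plan states no figure on this point. The check applies both rules to every possible score and then counts the ways of reaching the score where they differ.

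**Step 1. The two rules side by side** (Section 6.4 text; Table 9, Child-Pugh row; score range 5-15 from Appendix 2)

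| Score | Text | Table 9 | Agree? |
|---|---|---|---|
| 5-6 | Continue | No hold | Yes |
| 7 | Delay | No hold; an existing hold ends | **No** |
| 8-15 | Delay | Hold | Yes |

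The rules differ at one score out of eleven.

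**Step 2. First hold.** Take bilirubin 40 umol/L (2 points) and albumin 30 g/L (2 points), with INR below 1.7, no ascites and no encephalopathy (1 point each). The score is 2 + 2 + 1 + 1 + 1 = 7. The text calls for a delay. The Child-Pugh row of Table 9 is not triggered, and its bilirubin 22-51 row says to carry on.

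**Step 3. Restart.** A patient goes to 8, is held, and recovers to 7. Table 9 ends the hold. The text allows radiation again only once the problem has resolved. The natural reading is a return to A5-6, which 7 is not.

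**Step 4. How many point patterns give 7.** With ascites and encephalopathy at 1 point each, as at entry, bilirubin + albumin + INR must equal 7 - 2 = 5. The solutions (bilirubin, albumin, INR) are (1,1,3), (1,2,2), (1,3,1), (2,1,2), (2,2,1) and (3,1,1), which makes 6.

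- Bilirubin at 3 points (above 51): 1 pattern. The separate bilirubin hold covers it.
- Bilirubin at 1 or 2 points: 6 - 1 = 5 patterns. Among the liver rows, these rest on the Child-Pugh rule.
- Bilirubin at 2 points (34-51): 2 of those 5. Here Table 9 also says to carry on.

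If ascites and encephalopathy may vary as well, the counts are 15 in all, 1 with bilirubin above 51, 14 without, and 4 with bilirubin at 34-51. These are counts of patterns, not probabilities.

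**The case against.** The strongest reply is that the text can be read as the governing rule. Table 9 is titled as a set of suggestions. The text adds that a delay should be considered even when the table's criteria are not met, so the table is not the outer limit. The treating physician must also recommend going on. In addition, Table 9 has no row that says to treat at 7. The explicit instruction to carry on comes from the bilirubin row, and the rows are specific to one toxicity each.

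Part of this stands. A cautious reader would follow the text, and the restart conflict rests on a natural reading because the text gives no restart score. The conflict remains, however. A suggestion that contradicts the text is not ranked below it by its title. The clause on considering a delay is discretionary and tied to rapid liver change or investigator concern. The physician's recommendation is an added condition and does not waive A5-6. The Child-Pugh row is also not neutral at 7: a patient held for a score of 7 already meets its release condition.

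A second reply is that other safeguards limit the harm. Under Section 6.2, bilirubin above 34 in a patient who started below 22 is a hepatic event that stops pembrolizumab, requires notice to the sponsor within 24 hours and requires evaluation, with a hepatologist's opinion, within 72 hours. That is true, but it governs the drug and not SBRT. It also misses some patients: with a baseline of 22, the doubling rule needs 2 x 22 = 44, so a bilirubin of 40 would not trigger it.

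A third reply is that exposure is small. The course is short, and only one score is scheduled during it, near the start. The Child-Pugh declines reported in Section 2.2.2 are at about 3 months. This is fair, and it limits how much weight the point can carry.

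**Conclusion.** The concern holds. Section 6.4 contains two Child-Pugh rules for SBRT that conflict at a score of 7, and no part of the protocol ranks them. At first hold the mismatch in thresholds is explicit. At restart it depends on reading resolution as a return to A5-6. Compliance can still be checked at 5-6 and at 8 or more; only 7 is unsettled.

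The documents do not say how often a score of 7 will occur during SBRT, and no rate is assumed here. The response-rate analysis, the two-stage design and the other radiation deviation categories (duration, target dose, organ dose, mean liver dose) are untouched. The point should be corrected because it concerns liver safety and the correction is small.

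**What to change.** Change the Child-Pugh row of Table 9 to: score of 7 or more, hold radiation until it improves to 6 or less. This matches the text and the entry criterion. Add one sentence saying that a hold in any row overrides an instruction to carry on in another, because bilirubin of 34-51 can coexist with a score of 7. If the investigators do mean to treat at 7, change the text to a Child-Pugh score of 7 or less and leave the Child-Pugh row as it is. Which threshold is right is a clinical decision, but only one should appear.

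The cost is one table row and one sentence. Compared with following Table 9, holding at 7 may delay a few more courses. The duration rule in Section 5.1.2.6 already grades this: 16 to 21 calendar days is an acceptable variation and 22 or more is an unacceptable deviation. A slow recovery could therefore push a course past that limit or leave it incomplete. The existing text, taken as written, already carries that risk.
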